Appendix 3: Strength tests

3a: Sit to stand test

Test Administration:

- Place the chair against a wall or otherwise stabilise for safety
- Read the following script to the participant:
 - This is a test of how quickly you can stand up and sit down five times.
 - You need to sit in the centre of the seat with your feet shoulder width apart and flat on the floor.
 - You need to cross your arms at your wrists and hold them close to your chest.
 - You need to stand up completely, and make firm contact with the chair when you sit down
 - Do not use your hands to push from the chair
 - Do not to touch the back of the chair during the test
 - Try not to talk during the test as this may make you breathless
 - *I will now demonstrate the five repetitions [assume correct position and complete the full five repetitions].*
 - Do you think you are able to do that today? [document consent]
 - I would now like you to do two practice repetitions please stand up and sit down twice [patient does their practice]
 - Now we'll do the test so please stand up and sit down five times as quickly as you can when I say 'Go'
- Patient starts from sitting.
- Start the stopwatch at 'Go' and stop it when the buttocks touch the chair after the 5th repetition
- Record time on CRF
- Record any deviations from SOP, e.g. inability to complete 5 repetitions without assistance or use of arm support, any modifications should be documented

Norms for Community Dwelling Adults: (79)

[figure not shown]
Descriptive statistics for time (sec) for 5 sit-to-stand repetitions

Measurement (n)	Mean + SD	Minimum-Maximum
Trial 1: all ages (94)	7.8 + 2.8	4.0 - 16.3
Trial 2: all ages (94)	7.5 + 2.8	4.0 - 17.0
Mean: all ages (94)	7.6 + 2.7	4.0 - 16.0
Mean: 19-49 years (39)	6.2 + 1.3	4.1 - 11.5
Mean: 50-59 years (15)	7.1 + 1.5	4.4 - 9.1
Mean: 60-69 years (18)	8.1 + 3.1	4.0 - 15.1
Mean: 70-79 years (16)	10.0 + 3.1	4.5 – 15.5
Mean: 80-89 years (6)	10.6 + 3.4	7.8 - 16.0

3b: Hand grip dynamometer

American Society of Hand Therapists method (95).

- Patient should be in a seated position with shoulder adducted (arm against side) and elbow in a 90[°] flexion.
- Gentle, not a quick squeeze (that could cause needle to jump)
- Take the value in kilograms (on the outside of the dial).
- Take three readings for each arm (alternate arms so that each arm has a short rest between readings).

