5.2 Secondary objectives

- 1. Self-reported toxicity according to the Common Terminology Criteria for Adverse Events version 4 (CTCAE v4)
- 2. Taxane neuropathy assessed with the VibraTip (McCallan Medical Ltd, Northamptonshire)
- 3. Abdominal muscle and fat cross sectional areas at the L3 level in CT scans.
- 4. Quality of life & fatigue using the FACT-B, FACT-ES (74), FACT-F (75) and FACT-BP (78) for bone pain, hospital anxiety and depression scale (76) in all patients and also: - FACT-taxane scale for patients receiving taxanes (77)
- 5. Muscle strength in the lower and upper limb. Lower limb strength from five repetition sit to stand test (FRSTST) (79). Upper limb strength assessed with hand grip dynamometry (80)
- 6. Fidelity of the interventions. Self -reported dietary intake (7 day food diary or diet history over the phone) and resistance exercise
- 7. Changes in concomitant medication
- 8. Change in blood protein biomarkers (proteomics) (Sub study 1)
- 9. Change in insulin resistance with HOMA from fasting insulin and glucose (81) (Sub study 1)
- 10. Time to Treatment Failure (TTF), i.e. the time from randomisation to disease progression, death or discontinuation of therapy due to toxicity
- 11. Objective response and clinical benefit rate (objective response plus stable disease for ≥6 months) between treatment groups
- 12. Overall survival

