It is important that we ensure the safety of the intermittent diet in these advanced breast cancer patients particularly to ensure they do not lose lean body (largely muscle) mass as outlined above (52). Abdominal muscle and fat areas have been used in previous studies to predict toxicity and prognosis in advanced breast cancer patients receiving chemotherapy (52). We do not anticipate loss of lean body mass with the IER and resistance exercise intervention but need to document this. We plan to assess changes in abdominal muscle and fat in the cross sectional area at the L3 region in CT scans which are routinely conducted to assess their response to chemotherapy. These scans will be undertaken at intervals as defined above. If chemotherapy is stopped, e.g. due to excess toxicities, CT scans will revert to standard of care in the participant's chemotherapy centre, which is usually around every 12 weeks.

Thus assessing CT muscle and fat does not require any additional scanning time hence reducing the cost of the trial and the burden to patients.

CT measures of lean and fat mass will be obtained from the CT scans by our trial radiologists. Muscle and fat cross-sectional areas will be measured at the level of the L3 transverse processes using image analysis software such as Analyze 11.0 (AnalyzeDirect, Inc. Cheshire UK). Abdominal muscles at L3 include the psoas, paraspinal muscles (erector spinae, quadratus lumborum) and the abdominal wall muscles (transversus abdominus, external andinternal obliques, rectus abdominus). Abdominal muscle mass has been used to estimate total lean body mass in advanced cancer patients using the equation described by Mourtzakis et al (LBM (kg) = $0.30 \times [\text{skeletal muscle at L3 using CT (cm2)}] + 6.06)$ (88). This method will be insensitive to any changes in lean body mass which may be occurring in the upper and lower limbs, hence we are also including functional assessments of upper and lower muscle strength in the trial (79).

Oedema is a well-recognised side-effect of treatment with taxanes, and this may therefore interfere with body composition analysis using the CT method described above. In order to measure and correct for this attenuation values of subcutaneous fat and also the psoas muscles on the serial CT scans will be recorded using standardised regions of interest.

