The following 2 assessments will be assessed at baseline, at the start of cycle 3, and then every 3 cycles thereafter whilst patients remain in the trial i¹.

If cycles are delayed these assessments will be pushed back to coincide with day 1 of each chemotherapy cycle.

4. Quality of life fatigue, anxiety and depression

These will be estimated using the FACT-B, FACT-ES (74), FACT-F (75), FACT-BP for bone pain (78), and HAD scales (76) in all patients. The FACT-Taxane scale for patients receiving taxanes. Questionnaires will be completed by patients when they attend their chemotherapy unit (77).

5. Muscle strength.

Lower limb strength will be assessed from five repetition sit to stand test (FRSTST), normalised by weight (79) (Appendix 3). Arm muscular strength will be assessed using hand grip dynamometer. Both tests will be assessed at baseline, and at cycle 3 and every three cycles thereafter during the study by the B-AHEAD 3 study team or research nurses in the recruiting centres, who have been trained to undertake assessments according to the trial standard operating procedure (Appendix 3).

- 6. Fidelity of the interventions. Adherence to the diet and exercise interventions
- The intervention group will be asked to record compliance to the IER diet each week during the study using a specially designed self-monitoring diary. They will be asked to record whether they have managed to undertake two, one or no restricted days that week. Compliance to the intervention will be checked and recorded as part of the three weekly calls from their B-AHEAD 3 advisor.
- Both groups will be asked to record compliance with the resistance exercise in a special trial diary and the number of sessions achieved each week for the first 18 weeks of chemotherapy only. This diary will ask patients to record pain pre and post as assessed by Cormie et al (65). The diet and exercise diaries will monitor fidelity with the interventions and also act as a behavioural tool to increase compliance and a record of any problems encountered when they try to follow an exercise programme.
- We will record receipt of the three weekly phone calls from the trial dietitian and physiotherapist / cancer exercise specialist in the intervention group and from the physiotherapist / cancer exercise specialist in the exercise only group, which are part of the diet and exercise interventions.

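### The grip-strength procedure in Appendix 3b calls for a gentle squeeze and never asks for maximal effort, so followed literally it could give submaximal, inconsistent readings.

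*Protocol*

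**What the plan says.** Upper-limb strength is part of secondary objective 5 in Protocol section 5.2: "Upper limb strength assessed with hand grip dynamometry (80". Section 8.1.2, item 5, repeats it as an outcome: "Arm muscular strength will be assessed using hand grip dynamometer". The test is done at baseline, at cycle 3 and every three cycles after that, by the study team or by research nurses in the recruiting centres, "who have been trained to undertake assessments according to the trial standard operating procedure (Appendix 3". Appendix 3 is therefore the text that testers are trained on.

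Appendix 3b opens with "American Society of Hand Therapists method (95" and then has four bullets:

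- the posture of the patient and her arm;
- "Gentle, not a quick squeeze (that could cause needle to jump";
- reading the dial in kilograms;
- "Take three readings for each arm (alternate arms so that each arm has a short rest between readings".

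Appendix 3a, for the sit-to-stand test, has a script to be read aloud, a demonstration, practice repetitions and an explicit effort instruction: "please stand up and sit down five times as quickly as you can when I say 'Go".

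Section 8.1.2, item 3, explains why the strength tests are in the trial. The CT measure at L3 will not register changes in the arms and legs, "hence we are also including functional assessments of upper and lower muscle strength in the trial (79".

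**The concern.** A grip reading stands for muscle strength only if the person squeezes as hard as she can. If she stops short, the reading is her strength multiplied by the share of it that she chose to use. The protocol sets no target for that share, and the one adjective it offers points downward.

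Two things follow if testers take the bullet at its word. First, the share used can change from visit to visit and from tester to tester, which widens the spread of the change scores. Section 6.3 starts with 11 units and allows more. Second, a real loss of arm strength on the restricted diet would be harder to see. Sections 8.1.2 and 16.2 treat loss of lean mass under the diet as a safety question, and grip is the only upper-limb strength test among the outcome measures.

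This is not a detail that an analysis plan can supply later. Effort is fixed when the reading is taken, and no model recovers it afterwards.

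**Working it through.** The protocol gives no figure for this endpoint (no expected change, standard deviation or power), so there is nothing to reproduce. The check is a comparison of texts.

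**Step 1: is maximal effort requested anywhere?**

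| Place in the protocol | What it says on grip | Maximal effort requested? |
|---|---|---|
| 5.2, objective 5 | names the test | no |
| 8.1.2, item 3 | gives the reason for limb strength tests | no |
| 8.1.2, item 5 | timing, testers, pointer to Appendix 3 | no |
| Appendix 1 | lists grip among baseline assessments | no |
| Appendix 3b | posture, gentle squeeze, units, three readings per arm | no |
| Appendix 7 | timing, place, tester | no |

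**Step 2: what does the bullet govern?** It contrasts gentle with quick and gives needle jump as the reason. Needle jump comes from sudden force, so the natural reading concerns the speed at which force is applied. The bullet does not expressly ask for low force. It does not ask for full force either, and gentle is the only word in the procedure that bears on force at all.

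**Step 3: compare the two halves of Appendix 3.** The sit-to-stand test fixes effort in words that the tester reads out. The grip test has notes to the tester, no script and no effort target. The two tests serve the same objective and are done at the same visits.

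**Step 4: does the named method close the gap?** The heading line cites reference 95, which the reference list describes as a meta-analysis of normal values for grip. The method's content is not reproduced, so the protocol does not show whether it supplies an effort instruction.

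**Step 5: how would variable effort enter a change score?** Write each reading on the log scale as log(maximum) + log(share used). Then

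change in reading = change in log(maximum) + change in log(share used).

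Let *s* be the SD of the true change and *e* the SD of log(share) at each visit. Let *r* be the correlation of log(share) between visits, and take effort as unrelated to the true change. Then

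variance of change = *s*² + 2*e*²(1 − *r*).

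If each woman uses the same share every time (*r* = 1), the added term is zero. If her share is unrelated between visits (*r* = 0), the added term is 2*e*². The protocol gives none of *s*, *e* and *r*, so the direction (more noise, never less) is clear but the size is not.

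**The case against.** The strongest reply is that the bullet is a handling note and not an effort target. It sits under a named standard method, it is addressed to trained testers, and the outcome is called strength throughout. A tester who knows the method may well ask for a full squeeze and use the bullet only to prevent a jerk. Appendix 3b also has no participant script, so the protocol does not show what women are actually told. All of this stands. It limits the point to what could happen if the wording is followed literally.

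It does not remove the point. The protocol says that training follows Appendix 3, and the cited method is not reproduced there. In section 8.1.2, item 2, the protocol chose its vibration device for neuropathy because different nurses would do the testing and the stimulus had to be reproducible. The same reasoning applies to grip.

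Three stronger readings are tempting and are not supported:

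- *The endpoint measures chosen effort and not strength.* The contrast with quick and the needle-jump reason point to smooth rather than weak, so this cannot be stated as fact.
- *Unblinded testers will bias the comparison.* Section 6.5 says that all staff who assess endpoints are blinded. The roles it then lists do not include strength testers, and study team members may do the tests. Unblinding is therefore possible but not established.
- *A stated share of the effective sample size is lost.* Any such figure would come entirely from assumed values of *s*, *e* and *r*.

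The reach is also limited. Sit-to-stand covers the legs with a proper effort instruction, and serial CT watches for sarcopenia (sections 9 and 16.2).

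**Conclusion.** The point holds as a wording defect in the procedure for one secondary endpoint. Appendix 3b does not ask for maximal effort, no other part of the protocol does so for grip, and the one word on force suggests less than maximum. If testers follow it literally, readings could be submaximal and could vary between testers, centres and visits, which would add noise and make a change in arm strength harder to detect.

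This rests on two assumptions: that some testers would take the bullet at face value, and that the cited method, as taught, does not already correct it. Neither can be settled from the protocol. No effect size can be given. The primary analysis of progression-free survival and the sample size do not depend on it. How the three readings per arm are combined may properly be left to the analysis plan and is not part of this point.

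**What to change.** Replace the second bullet of Appendix 3b with an instruction such as: *Squeeze smoothly, building up to as hard as you can, without jerking.* Have every tester read it out from the same short script, as Appendix 3a already does for sit-to-stand. Record on the case report form which version of the instruction was used for each assessment.

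The cost is one line of protocol text, a note to testers and one extra field. The downside is that readings taken before the change used the old wording, so a woman tested under both versions could show a change due to the instruction alone. The recorded version lets the analysis see this, but cannot undo it.

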Appendix 4: Standard 3 weekly diet mailings which can be sent to the IER group.

Mailing	Торіс
1	Ways to get motivated for changing your diet
	• Listing pros and cons (decisional balance)
	Increasing your confidence
	Goal setting: short, intermediate and long term
	Sharing tips to get and stay motivated
	• Finding support.
	Overcoming barriers
2	Energy balance: energy restriction
	Possible benefits of energy restriction
	Weight gain and energy balance
	• Body fat and health and where fat is stored
	• Energy density of food
3	The Mediterranean diet
	• What is a Mediterranean diet?
	• 5-a-day
	• Supplements and vitamins
	• Fibre including ready reckoner done for book
4	Tips for following a diet during chemotherapy
	• Diet and energy related side effects
	• Fatigue
	• Getting enough sleep
	• Planning
5	Healthy cooking
	• Healthy cooking methods
	• Simple recipes
	• Healthy snacking, packed lunches
6	Mood and hunger, food cravings
	• Dealing with cravings
	• Treating yourself in ways other than food
	Gaining control over eating
	• Stress mood and food (use some tips from bahead 2 problem solving sheet)
7	Tips for shopping and eating out
.	

	Healthy options for eating out		
	• Shopping		
	• Reading and understanding food labels		
8	How to make the 2 day diet work for you		
9	Drinks and sauces		
	• Alcohol		
	• Caffeine		
	• Fizzy drinks		
	• Sweeteners		
	• Fructose		
	Sauce info		
10	Diet myths		

Appendix 5: Serum and plasma collection, handling and storage

Sample collection

Baseline blood samples will be collected at MFT or chemotherapy centres before initiating the diet and exercise programmes. The two sub-study 1 samples will be collected in the chemotherapy centres two days before chemotherapy (this may coincide with the time of normal pre-treatment blood tests for women on paclitaxel) and on the day of chemotherapy treatment. Women will be asked to fast for 12 hours and they will receive a complimentary light breakfast immediately after blood collection if at MFT. Samples will be spun, aliquoted and processed and stored at -80°C at MFT or in the chemotherapy centres.

Biohazards and safety requirements to be met with the handling of all human blood samples; the procurement, handling and storage of blood specimens will be undertaken by personnel who have received training in the risks associated and safety requirements. Standard operating procedures are in place to comply with good clinical practice and good laboratory practice.

Insulin serum SST (BD Vacutainer: orange top)

Samples should be centrifuged as soon as possible after collection to separate the serum from the cells. Serum can then be stored for 24 hrs at 2-8°C or 1 month at -15 to -25°C before storing at -80°C. Insulin samples will be stored at -80°C at the site of collection then transported for analysis to MFT. Insulin will be measured by clinical biochemistry at MFT using a commercially available chemoluminescence immunoassay. All assays will be batched and performed on stored serum (-80°C) upon completion of the study to reduce inter-batch variation.

Glucose fluoride (BD Vacutainer: grey top)

Glucose will be assessed using a Hexokinase/glucose-6-phosphate dehydrogenase method. This will be analysed in the recruiting centres or at MFT as soon as possible or stored at 4°C. Freezing and long term storage of these samples is not recommended.

Plasma collection and storage for proteomic analysis (BD Vacutainer: purple top)

Sample for proteomic analysis will be collected in EDTA tubes (10ml tube or 3 x 4ml tube or equivalent). After collection the tube should be inverted 8-10 times and spun within 30 minutes. Centrifugation will be for 10 minutes at 2000g with plasma removed from the upper layer. After preparation the sample

B-AHEAD 3 | Protocol | v7.0 | 02/10/18 | Page 47

will be split into 2ml aliquots and frozen. Storage will be at -80°C at the site of collection with any transport under dry ice to ensure samples don't thaw. Proteomic analysis will be carried out by [name] in the Institute of Cancer Sciences at the University of Manchester after all samples have been collected.

[figure not shown]
Collection, storage and transport of serum and plasma samples

If possible, blood samples will be taken at all of the recruiting hospitals where -80°C storage facilities exist. Samples will be stored at -80°C at the site of collection until transportation to The Nightingale Centre at MFT The plasma samples will then be collated and transported to [name] in the Institute of Cancer Sciences at the University of Manchester. Samples will be anonymised by assignment of a study code and logged to a database prior to storage and /or delivery to the laboratories where the research will be performed. A copy of the sampling log that will not contain any identifiable information will accompany samples.

Responsibility for transfer of samples

The B-AHEAD 3 Study team at MFT will be responsible for monitoring transfer and receipt of biological specimens. Tracking forms will be sent by centres to the B-AHEAD 3 Study team at MFT to monitor the transfer of all biological samples. All data will be handled, computerised and stored in accordance with the Data Protection Act 1998. Any transported samples should be kept frozen during the transport.

Appendix 6: Blood sampling SOP for B-AHEAD 3 staff at Manchester University NHS Foundation Trust

Notes:

- All blood ideally from arm opposite to lymph node surgery.

- *suitable clinician could be a surgeon, doctor, nurse or phlebotomist with good experience of taking blood samples.

- Participants will have a maximum of 5 attempts at blood collection.

Appendix 7: Schedule of assessments in the B-AHEAD 3 trial

Intervention and control patients				
Assessment	Timing	Location	Undertaken by	
CT scan for assessment of response	Usually every 3 cycles	Local hospital	Organised by research	
and lean body mass	as per local guidelines		nurse	
Self-report CTCAE v4	At each	Chemotherapy units	NIHR research nurse	
(chemotherapy toxicity)	chemotherapy cycle			
Taxane neuropathy with vibratip	At each	Chemotherapy units	NIHR research nurse	
	chemotherapy cycle			
Quality of life & fatigue, hospital	Baseline, then every 3	Chemotherapy units	NIHR research nurse	
anxiety depression score	cycles			
Fasting insulin & glucose, protein	Baseline (and twice	Chemotherapy units	NIHR research nurse	
blood-based biomarkers	around cycle 3 or 4 if	or Prevent Breast Cancer	or B-AHEAD 3 researcher	
	on sub-study 1)	Research Unit		
		according to patient		
		preference		
Lower limb & upper limb strength	Baseline, then every 3	Prevent Breast Cancer	NIHR research nurse or	
from sit to stand and hand grip	cycles	Research Unit or	B-AHEAD 3 researcher	
dynamometer tests		chemotherapy units		
7 day food diary and physical activity	Baseline, cycle 3 and	Completed by patient at	Checked by B-AHEAD 3	
questionnaire	cycle 6	home & e-mailed /	researcher	
		posted back to the		
		B-AHEAD 3 researchers		
Demographics,	Baseline	Prevent Breast Cancer	B-AHEAD 3 researcher	
weight and medical history		Research Unit or over		
		phone		
Exercise tracker	Weekly throughout	Patient to complete at	Patient to complete at	
	trial for the first 18	home	home	
	weeks of			
	chemotherapy			

Intervention group				
Advice	Timing	Location	Undertaken by	
Diet advice for intervention group	Baseline	Prevent Breast Cancer Research Unit or over phone	B-AHEAD 3 dietitian	
Resistance exercise advice	Baseline	Prevent Breast Cancer Research Unit or Skype (or similar application) or over phone or at local unit	B-AHEAD 3 physiotherapist / cancer exercise specialist / local physiotherapist	
Review calls to discuss diet & exercise	3 weekly whilst in the trial	Patients called at home	B-AHEAD 3 dietitian	
Review call / Skype to discuss resistance exercise	At 3 weeks	Patients called at home	B-AHEAD 3 physiotherapist / cancer exercise specialist	

Control group				
Advice	Timing	location	Undertaken by	
Resistance exercise advice	Baseline	Prevent Breast Cancer Research Unit or Skype (or similar application) or over phone or at local unit	B-AHEAD 3 physiotherapist / cancer exercise specialist / local physiotherapist	
Review calls / Skype to discuss resistance exercise	3 weekly whilst in the trial	Patients called at home	B-AHEAD 3 physiotherapist / cancer exercise specialist	

